9.3.4 Removal of Subjects from Treatment or Assessment

Withdrawn subjects are those who do not complete all evaluations and procedures outlined in the protocol. Subjects who discontinue taking study drug for any reason must also be withdrawn from the study. All adverse events that are present when the subject withdraws from the study will be followed as described in [Section 9.6.2.1](#).

Subjects must be withdrawn from the study for any of the following events:

- Elevated AST or ALT 3 times upper limit of normal (ULN) or greater and elevated bilirubin greater than 2 times ULN and no other explanation of these abnormal tests
- An SAE assessed as related to study treatment by the Investigator or Medical Monitor
- Clinically significant worsening of acne status requiring change of treatment in acne management (eg. increased size or number of nodules)

Subjects may be withdrawn from the study for one of the following events:

- Adverse Event: An AE that, in the opinion of the Investigator or Sponsor, suggests that continued participation in the study is not in the subject's best interest for safety reasons. Only a primary AE leading to withdrawal should be noted to be the reason for withdrawal.
- Abnormal Laboratory Result: Any clinically significant laboratory abnormality that requires withdrawal of the subject from the study should be considered an AE leading to withdrawal. If possible, laboratory tests will be repeated for any results that were clinically significantly abnormal until the abnormality is resolved or stabilized to the satisfaction of the Investigator in consultation with the Medical Monitor.
- Lost to Follow-up: Confirmed at minimum by 2 phone calls and a traceable letter without answer.
- Subject Request: Subject requests for any reason to be withdrawn or withdraws his/her consent.
- Protocol Deviation: A subject may be withdrawn from the study at the discretion of the Investigator or Sponsor due to poor compliance with protocol requirements that may compromise the study results or subject safety.
- Other: Other reasons include but are not limited to: Investigator decision that it is in the subject's best interest to be withdrawn, administrative reasons, relocation of subject, etc. If a subject becomes pregnant during the study, the subject will be withdrawn from the study and followed through to the conclusion of the pregnancy.

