9.6.2.2 Clinical Laboratory Evaluations

Clinical laboratory evaluations (chemistries, hematology, lipid profile, thyroid hormones and urinalysis) outlined in [Appendix 2](#) will be performed on all subjects prior to enrollment to verify eligibility. Clinical laboratory evaluations will be repeated at Visit 1 and at Visit 4/ET to identify changes that may have occurred as a result of participation in the study. If a clinically significantly abnormal laboratory result is a reason for a subject being withdrawn from the study or requiring treatment for the abnormality, this abnormal result must also be reported as an adverse event.

Urine pregnancy test will be performed on females of childbearing potential only at each visit.

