11.6.3 Clinical Laboratory Evaluations

Continuous clinical laboratory analytes will be summarized by **double-blind** treatment, analyte, and visit using descriptive statistics. Categorical laboratory analytes, classified as normal or abnormal, will be summarized by treatment analyte, and visit using the number and percentage of subjects in each category. The denominators for calculating the

percentages will be based on the number of subjects in each treatment with non-missing assessments at a particular visit for the Safety population.

Shifts to values outside of the normal range will be presented by treatment and analyte and will be summarized by the number and percentage of subjects with evaluable shifts. An evaluable shift is one where both the Screening Visit value and the on-treatment value or early termination value are recorded. The denominators for calculating the percentages will be based on the number of subjects in each treatment group who have an evaluable shift for a particular analyte.

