11.2 CLINICAL LABORATORY PARAMETERS

Descriptive statistics for clinical laboratory values (in SI units) and changes from the baseline values at each assessment time point will be presented by double-blind treatment group for the following laboratory analytes:

Hematology: Hemoglobin, hematocrit, red blood cell count, mean cell volume, white blood cell count, white blood cell count differential, and platelet count

Chemistry: albumin, alanine aminotransferase, aspartate aminotransferase, blood urea nitrogen, gamma glutamyl transferase, glucose, lactate, dehydrogenase, total bilirubin, creatine phosphokinase, total protein, serum creatinine, sodium potassium, calcium, chloride, bicarbonate, and phosphorus

Urinalysis: color, specific gravity, potential for hydrogen (pH), leukocytes, ketones, protein, glucose, blood, and bilirubin

Lipid Profile: total cholesterol and triglycerides

Thyroid Function: thyroid stimulating hormone and free T4 and T3

Other Urine pregnancy test

Continuous clinical laboratory analytes will be summarized by double-blind treatment, analyte, and visit using descriptive statistics. Categorical laboratory analytes, classified as normal or abnormal (low or high), will be summarized by double-blind treatment group,

Clinical laboratory test values will be considered potentially clinically significant (PCS) if they meet either the lower-limit or higher-limit criteria provided by the [REDACTED]

[REDACTED] (Appendix 1). The number and percentage of subjects who have PCS postbaseline clinical laboratory values will be tabulated by double-blind treatment group for the treatment period. The percentages will be calculated relative to the number of subjects with available non-PCS baseline values and at least 1 postbaseline assessment for the treatment period. The numerator will be the total number of subjects with available non-PCS baseline values and at least 1 PCS postbaseline value for the treatment period. A supportive tabular display of subjects with PCS postbaseline values will be provided, including SID, study center number, and baseline and all postbaseline (including non-PCS) values.

In addition, a tabular display showing all AEs that occurred in subjects who had PCS postbaseline clinical laboratory values will be provided.

Shift tables from baseline to end of the double-blind study period for clinical laboratory parameters will be presented by treatment group for the following categories: low, normal, and high.

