Statistical analyses will be performed using version 9.3 (or newer) of SAS on a LINUX operating system.

16.0

DATA HANDLING CONVENTIONS

16.1

VISIT TIME WINDOWS

Table 16.1–1 presents the visits assigned for efficacy and safety analyses and the corresponding range of treatment days (window) during which an actual visit may occur.

Table 16.1–1. Visit Time Windows

Derived Visit	Scheduled Visit Day^a	Window
Baseline	Day 1	Days \leq 1
Week 3	Day 22	Days [2, 32]
Week 6	Day 43	Days [33, 53]
Week 9	Day 64	Days [54, 74]
Week 12	Day 85	Days \geq 75
End of study ^b	Final or Termination Visit during the treatment period	

a Relative to the date of the first dose of the investigational product or date of randomization if patient did not receive any dose. Day 1 = the date of the first dose of the investigational product (or date of randomization if patient did not receive a dose). There is no Day 0.

b Presented in analysis tables for safety parameters, including but not limited to electrocardiograms, clinical laboratory values, and vital signs.

If the assessment date (if the assessment date is unavailable, using visit date instead) is on or after the date of the first dose of the investigational product, the study day is calculated by assessment date – date of the first dose of the investigational product + 1. If the assessment date is before the date of the first dose of the investigational product, the study day is calculated by assessment date – date of the first dose of the investigational product. Therefore, a negative day indicates a day before the start of the investigational product.

If a subject has 2 or more visits within the same window, the last visit with a nonmissing value will be used for analysis.

16.2

MISSING DATA HANDLING FOR PRIMARY AND SECONDARY EFFICACY ENDPOINTS

For the co-primary and secondary efficacy analyses, the primary missing data imputation method is multiple imputation, as outlined in the following procedures:

- o The SAS PROC MI procedure with a fully conditional specifications (FCS) method will be used to create 20 imputations. The FCS is proposed as it allows for accommodation of categorical variables and it has the versatility to handle arbitrary missing data patterns. Based on these 20 imputations, the relative efficiency will be 0.995 for 10% of missing data and 0.990 for 20% of missing data (Rubin, 1976, 1987, 1996) .

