16.3 REPEATED OR UNSCHEDULED ASSESSMENTS OF SAFETY PARAMETERS

If a subject has repeated assessments before the start of investigational product, the results from the final nonmissing assessment made before the start of the investigational product will be used as baseline. If end-of-study assessments are repeated or if unscheduled visits occur, the last nonmissing postbaseline assessment will be used as the end-of-study assessment for generating summary statistics. However, all postbaseline assessments will be used for PCS value determinations, and all assessments will be presented in the data listings.

16.4**MISSING DATE OF THE LAST DOSE OF INVESTIGATIONAL PRODUCT**

When the date of the last dose of the investigational product is missing for a subject in the Safety Population, all efforts should be made to obtain the date from the Investigator. If after all efforts are made it is still missing, the last available dosing record date will be used as the last dose date.

16.5**MISSING SEVERITY ASSESSMENT FOR ADVERSE EVENTS**

If severity is missing for an AE that started before the date of the first dose of the investigational product, an intensity of mild will be assigned. If severity is missing for an AE that started on or after the date of the first dose of the investigational product, an intensity of severe will be assigned. The imputed values for severity assessment will be used for the incidence summary; the values will be shown as missing in the data listings.

16.6**MISSING RELATIONSHIP TO INVESTIGATIONAL PRODUCT FOR ADVERSE EVENTS**

If the relationship to study treatment is missing for an AE that started on or after the date of the first dose of the investigational product, a relationship of related will be assigned. The imputed values for relationship to study treatment will be used for the incidence summary; the values will be shown as missing in the data listings.

16.7**MISSING DATE INFORMATION FOR ADVERSE EVENTS**

The following imputation rules only apply to cases in which the start date for AEs is incomplete (ie, partly missing).

Missing month and day

- If the year of the incomplete start date is the same as the year of the first dose of the investigational product, the month and day of the first dose of the investigational product will be assigned to the missing fields
- If the year of the incomplete start date is before the year of the first dose of the investigational product, *December 31* will be assigned to the missing fields

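### SAP 16.3 lets a later, possibly off-treatment, repeat replace an abnormal Week 12 or early-termination laboratory value in the end-of-study summary and, on the natural reading, in the only laboratory shift table

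*SAP*

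**What the plan says.** Scheduled postbaseline laboratory sampling is sparse. Protocol 9.6.2.2: "Clinical laboratory evaluations will be repeated at Visit 1 and at Visit 4/ET". Visit 1 is Week 3 and Visit 4 is Week 12.

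Unscheduled sampling is prompted by results. In the item on abnormal laboratory results, Protocol 9.3.4 says that, if possible, "laboratory tests will be repeated for any results that were clinically significantly abnormal until the abnormality is resolved or stabilized". Protocol 9.6.2.1 also has the investigator follow an unresolved adverse event for at least 30 days after the final visit.

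The SAP has three rules on which value counts:

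- SAP 16.3, for repeated end-of-study assessments or unscheduled visits: "the last nonmissing postbaseline assessment will be used as the end-of-study assessment for generating summary statistics". The next sentence adds that "all postbaseline assessments will be used for PCS value determinations, and all assessments will be presented in the data listings".
- SAP Table 16.1-1 defines the End of study row, which its footnote assigns to safety tables including laboratory values, as "Final or Termination Visit during the treatment period".
- SAP 16.1, on analysis windows: "If a subject has 2 or more visits within the same window, the last visit with a nonmissing value will be used for analysis". The Week 12 window runs from Day 75 with no upper limit.

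SAP 11.2 plans one laboratory shift analysis: "Shift tables from baseline to end of the double-blind study period for clinical laboratory parameters will be presented by treatment group". Protocol 11.6.3 describes the shift differently: "An evaluable shift is one where both the Screening Visit value and the on-treatment value or early termination value are recorded".

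**The concern.** Retesting is not random. It happens because a value was abnormal and judged clinically significant, and it stops when the value has settled. A rule that takes the last available value therefore tends to replace abnormal values with better ones, and seldom the reverse. Since SAP 16.3 has no limit by last dose, the replacement may have been taken off drug, when a drug-related change would be expected to fade.

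Laboratory safety is part of the trial's secondary objective. The shift table is the between-arm display a reader would use to see how many subjects moved out of the normal range. If it rests on the last repeat, it understates those moves, and most of all for the abnormalities important enough to be retested.

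**Working it through.** The plan states no figure for this point, so there is none to reproduce. The check is a reading of the rules against each other, followed by an illustration with assumed rates.

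**1. One subject through each rule.** Take a hypothetical subject with last double-blind dose and Visit 4 on Day 85 (the scheduled Week 12 day). A laboratory value is normal at baseline, above range and clinically significant on Day 85, and normal on a repeat on Day 99. Day 99 is 14 days after the visit, inside the 30-day follow-up (85 + 30 = Day 115).

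| Rule | Value used | Result |
|---|---|---|
| SAP 16.3, end of study | Day 99 | normal |
| SAP 16.1, Week 12 window (Day 75 onward, last value) | Day 99 | normal |
| SAP Table 16.1-1, End of study row, read strictly | Day 85 | high |
| Protocol 11.6.3, on-treatment or early-termination value | Day 85 | high |
| SAP 16.3 and 11.2, PCS tables | all values | counted if Day 85 passes the PCS limit and baseline did not |

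The SAP thus gives two answers for the end-of-study value, and one of them disagrees with the protocol. The by-visit Week 12 row is no clean fallback, because its open-ended window also picks up the repeat.

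**2. Does it reach the shift table?** SAP 16.3 speaks of summary statistics and does not name shift tables, so this step is an inference. It is the natural one: SAP 11.2 runs the shift to the end of the double-blind period, and SAP 16.3 is the rule on which repeated or unscheduled safety value counts as end of study. SAP 11.2 plans no shift to the worst value and none to Week 3.

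**3. Size, by illustration only.** Let p be the true proportion with a Week 12 out-of-range shift in an arm, and r the share of those retested and normal by the last value. The table then shows p × (1 − r). Assume 500 per arm (the planned size), p = 6% on sarecycline and 3% on placebo, and the same r in both arms. The rates and r are assumptions; the documents give neither.

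| r | Sarecycline | Placebo | Difference |
|---|---|---|---|
| 0 | 30 (6.0%) | 15 (3.0%) | 3.0 points |
| 0.25 | 22.5 (4.5%) | 11.25 (2.25%) | 2.25 points |
| 0.50 | 15 (3.0%) | 7.5 (1.5%) | 1.5 points |
| 0.75 | 7.5 (1.5%) | 3.75 (0.75%) | 0.75 points |
| 1 | 0 | 0 | 0 |

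With equal r below 1 the absolute difference shrinks by (1 − r) and the ratio stays at 2. With unequal r the difference need not shrink: r = 0.25 on sarecycline and 0.50 on placebo gives 6% × 0.75 − 3% × 0.50 = 4.5% − 1.5% = 3.0 points. What holds in general is that each arm's shift rate is understated when r is above 0.

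Only clinically significant results come under the retest rule. Over a whole low/normal/high table, which counts every out-of-range value, r is probably small; it would be larger for the abnormalities that matter most.

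**The case against.** The case for leaving the plan alone has several sound parts.

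- **The retest rule is narrow.** A reader might infer that every abnormal result is retested until normal. The protocol says only if possible, covers only clinically significant results, and accepts stabilisation as an end point. A stabilised value can still be abnormal, so the last repeat is not normal by design. This stands.
- **The abnormal values are kept elsewhere.** A reader might infer that the rule erases the laboratory signal. It does not. All postbaseline values feed the PCS determinations and listings, subjects meeting the liver criteria are listed separately, and Protocol 9.6.2.2 requires an adverse event report when the abnormality leads to withdrawal or treatment. This stands, within limits. The PCS limits are not visible in the available text, so how much of the out-of-range range they cover is unknown. Listings are not between-arm summaries. A significant abnormality that normalises without withdrawal or treatment is outside that reporting requirement.
- **The SAP may already exclude late repeats.** Table 16.1-1 confines End of study to the treatment period, and SAP 11.2 refers to the double-blind period. On that reading the Day 99 repeat drops out. But SAP 16.3 then says something else, and a programmer following 16.3 would use Day 99. The objection turns the defect into a contradiction; it does not remove it.
- **Week 3.** An abnormality at Week 3 that is normal by Week 12 might look like another overwritten value. It is not: any baseline-to-end shift shows it that way, and by-visit summaries are planned. It is a gap in what the single shift table covers.
- **Protocol 11.6.3 does not ask for a worst-value shift.** It says when a shift can be evaluated. The worst-value table proposed below is a recommendation, not a protocol requirement.

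**Conclusion.** The point holds as a conflict between rules with a foreseeable direction of bias. Followed as written, SAP 16.3 allows a later and possibly off-treatment repeat to replace an abnormal Week 12 or early-termination value in the end-of-study summary. The open-ended Week 12 window has the same exposure. Extending this to the shift table rests on the natural reading of SAP 11.2, not on an explicit statement. SAP 16.3 also disagrees with Table 16.1-1 and with the basis for shifts in Protocol 11.6.3.

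The consequence is understated shifts and end-of-study summaries. The documents do not support the stronger claim that the trial would lose its laboratory safety signal, since the PCS tables, the listings and part of the adverse event reporting retain it. The size cannot be derived, because neither abnormality rates nor retest rates are given; the figures above show only how the effect scales. Severity is minor to moderate.

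**What to change.** 1. In SAP 16.3, 16.1 and 11.2, define the end-of-study and Week 12 laboratory value as the scheduled Visit 4/early-termination assessment or the last on-treatment value, with a stated cut-off relative to the last double-blind dose. Let a repeat replace it only when the original sample is documented as invalid. Show later repeats in listings only. A strict first-sample rule would be worse, because it would keep faulty samples.
2. Add a shift table from baseline to the worst on-treatment value, highest and lowest separately, using Week 3, Week 12/early-termination and unscheduled on-treatment samples.
3. Align SAP 16.3 with Table 16.1-1 and Protocol 11.6.3, so that one definition of end of study governs both summaries and shifts.

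The cost is SAP wording and one additional table, with no new data. SAP section 17.0 records an earlier SAP change made before database lock without a protocol amendment, so the route exists. The downside is somewhat higher reported abnormality rates. A worst-value table also gives subjects with more samples more chances to show an extreme, so it should sit beside the end-of-study shift table and not replace it.

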16.8 MISSING DATE INFORMATION FOR PRIOR OR CONCOMITANT MEDICATIONS

For prior or concomitant medications, including rescue medications, incomplete (ie, partly missing) start dates and/or stop dates will be imputed. When the start date and the stop date are both incomplete for a subject, the start date will be imputed first.

16.8.1 Incomplete Start Date

The following rules will be applied to impute the missing numeric fields for an incomplete prior or concomitant medication start date. If the stop date is complete (or imputed) and the imputed start date is after the stop date, the start date will be imputed using the stop date.

Missing month and day

- If the year of the incomplete start date is the same as the year of the first dose of the investigational product, the month and day of the first dose of the investigational product will be assigned to the missing fields

- If the year of the incomplete start date is before the year of the first dose of the investigational product, *December 31* will be assigned to the missing fields
- If the year of the incomplete start date is after the year of the first dose of the investigational product, *January 1* will be assigned to the missing fields

Missing month only

- If only the month is missing, the day will be treated as missing and both the month and the day will be replaced according to the above procedure

Missing day only

- If the month and year of the incomplete start date are the same as the month and year of the first dose of the investigational product, the day of the first dose of the investigational product will be assigned to the missing day
- If either the year of the incomplete start date is before the year of the date of the first dose of the investigational product or if both years are the same but the month of the incomplete start date is before the month of the date of the first dose of the investigational product, the last day of the month will be assigned to the missing day.
- If either the year of the incomplete start date is after the year of the date of the first dose of the investigational product or if both years are the same but the month of the incomplete start date is after the month of the date of the first dose of the investigational product, the first day of the month will be assigned to the missing day

16.8.2 Incomplete Stop Date

The following rules will be applied to impute the missing numeric fields for an incomplete prior or concomitant medication stop date. If the date of the last dose of the investigational product is missing, replace it with the last visit date in the imputations described below. If the imputed stop date is before the start date (imputed or nonimputed start date), the imputed stop date will be equal to the start date.

Missing month and day

- If the year of the incomplete stop date is the same as the year of the last dose of the investigational product, the month and day of the last dose of the investigational product will be assigned to the missing fields
- If the year of the incomplete stop date is before the year of the last dose of the investigational product, *December 31* will be assigned to the missing fields
- If the year of the incomplete stop date is after the year of the last dose of the investigational product, *January 1* will be assigned to the missing fields

Missing month only

- If only the month is missing, the day will be treated as missing and both the month and the day will be replaced according to the above procedure

Missing day only

- If the month and year of the incomplete stop date are the same as the month and year of the last dose of the investigational product, the day of the last dose of the investigational product will be assigned to the missing day
- If either the year of the incomplete stop date is before the year of the date of the last dose of the investigational product or if both years are the same but the month of the incomplete stop date is before the month of the date of the last dose of the investigational product, the last day of the month will be assigned to the missing day
- If either the year of the incomplete stop date is after the year of the date of the last dose of the investigational product or if both years are the same but the month of the incomplete stop date is after the month of the date of the last dose of the investigational product, the first day of the month will be assigned to the missing day

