9.4.6.2 Medication Washout Prior to Study Randomization

Subjects receiving excluded medications/therapies at screening may washout from those therapies to continue eligibility in the study as described in [Table 9-3](#). Under no circumstances should a subject be placed at risk by the withdrawal of a current medication.

Table 9-3: Medication Washout Requirements

Medication Type	Minimum Washout (days prior to SV2 baseline)
Medicated facial cleansers Topical acne treatments (other than those listed below)	7 days
Topical antibiotics and azelaic acid containing medication Topical non-prescription anti-inflammatories (other than those listed below)	2 weeks
Topical retinoids Topical corticosteroids Systemic antibiotics	4 weeks

Note: Use of systemic retinoids, systemic corticosteroids, or systemic androgens/anti-androgens within 12 weeks of **randomization** is exclusionary.

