1. Did not meet inclusion/exclusion criteria
2. Have taken any interfering concomitant medications
3. Duration of treatment less than 68 days, or did not complete study based on subject exit status, or overall study drug compliance less than 80%
4. Received treatment different from the assigned treatment

A list of subjects with conditions 1, 2, and 3 above prior to unblinding will be created. This list will be reviewed by a Clinical Representative to determine which subjects are to be excluded from the PP population. These subjects will then be documented in a signed memo prior to unblinding. The subjects who received treatment different from the assigned treatment (condition 4) will be identified after unblinding and will be documented in a separate signed memo.

Three “visit types” will be defined for the purposes of analysis and summaries:

- Observed Cases (OC) – includes assessments collected at each scheduled visit. All applicable efficacy and safety variables will be summarized for OC visits.

- Multiple Imputation Data – for the primary and secondary efficacy endpoints, missing data will be imputed using multiple imputation procedures further described in Section 16.2.
- LOCF – defined as the last post-baseline data recorded for each efficacy variable. This visit will be denoted as Week 12 (LOCF) and will only be used to summarize efficacy data. The LOCF visit provides missing value imputation for subjects who do not provide data for the Week 12 visit.

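### SAP 16.8.1 and 16.8.2 settle a start/stop conflict in opposite directions, and the start-first order lets a guessed start overwrite a stop month recorded before treatment

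*SAP*

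**What the plan says.** SAP 16.8 fixes the order for medication records: "When the start date and the stop date are both incomplete for a subject, the start date will be imputed first".

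SAP 16.8.1 covers a start with month and day missing. "If the year of the incomplete start date is the same as the year of the first dose of the investigational product", then "the month and day of the first dose of the investigational product will be assigned to the missing fields". It also has a conflict rule under which the start gives way to the stop: "If the stop date is complete (or imputed) and the imputed start date is after the stop date, the start date will be imputed using" that stop.

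SAP 16.8.2 covers a stop with only the day missing. If its month is before the last-dose month, "the last day of the month will be assigned to the missing day". Its conflict rule makes the stop give way: "If the imputed stop date is before the start date (imputed or nonimputed start date), the imputed stop date will be equal to the start".

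These dates decide whether a drug counts as prior or concomitant (SAP Section 8; Protocol 11.7.2). SAP 6.4 also lists, as a condition for exclusion from the per-protocol population, "Have taken any interfering concomitant medications".

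**The concern.** The two conflict rules disagree whenever both dates are imputed and the imputed start falls after the imputed stop. The order in 16.8 then selects the rule that discards the better information. The stop month was recorded; the start month and day were filled in by convention. In one pattern the result is a date that the record itself rules out: a drug recorded as stopped in a month before treatment is dated to the first-dose day.

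Drugs stopped shortly before dosing are expected in this trial. Protocol 9.4.6.2 says: "Subjects receiving excluded medications/therapies at screening may washout from those therapies to continue eligibility in the study". Protocol 9.4.6 collects acne drugs used in the 3 months before the first screening visit, and SAP Section 8 summarises prior and concomitant acne medications. The correctness of those tables is at stake, and so is whether two programmers following the SAP would produce the same ones.

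**Working it through.** The plan gives no figure to reproduce, so the check applies the rules as written. The dates below are assumed for illustration.

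**Example.** Start recorded as 2015 only; stop recorded as January 2015, day missing; first dose 20 March 2015; last dose in June 2015.

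| Step | Order stated in 16.8 | 16.8.1 rule prevails |
|---|---|---|
| Start imputed (year equals first-dose year) | 20 Mar 2015 | 20 Mar 2015 |
| Stop imputed (January precedes last-dose month) | 31 Jan 2015 | 31 Jan 2015 |
| Conflict settled | stop moved to 20 Mar | start moved to 31 Jan |
| Final record | 20 Mar to 20 Mar | 31 Jan to 31 Jan |
| Class, Protocol 11.7.2 | concomitant | prior |
| Class, SAP Section 8 read literally | neither | prior |

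The stop moves by 28 days (February) + 20 days (March) = 48 days from its imputed value, and out of its recorded month.

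**Why the 16.8.1 rule cannot help.** Its extension to imputed stops needs both dates to be incomplete. In that case the start is filled in first, when no imputed stop exists yet. Once 16.8.2 has acted the two dates are equal, so the start is no longer after the stop. In the stated order that extension never operates.

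**Classification.** SAP Section 8 calls a drug prior if it ended before the first-dose date. It calls a drug concomitant if it started after first dose, or started before it and either ended on or after that date or is ongoing. A record that starts and ends on the first-dose day meets none of these. Protocol 11.7.2 counts a start on or after the first-dose date, so there the record is concomitant.

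**Scope.** The rules were applied to a grid of assumed records: a mid-month first dose in each of 12 months of one year; a true stop 1 to 6 months before the first-dose month; a true start in the stop month or earlier, up to 11 months before the first-dose month. That gives (11 + 10 + 9 + 8 + 7 + 6) × 12 = 612 start/stop pairs, 251 starting in the first-dose year and 361 in an earlier year. Each pair was recorded in six ways: start complete, day missing or year only; stop complete or day missing.

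- Year-only start in the first-dose year with a day-missing stop: 251 of 251 end on the first-dose day in the stated order, and 0 of 251 if 16.8.1 prevails.
- Every other pattern in the grid: 0 records reach the first-dose day.
- A complete stop is protected because 16.8.1 then moves the start.
- A year-only start in an earlier year becomes 31 December of that year. The 16.8.2 overwrite can still shift such a stop (October 2014 becomes 31 December 2014), but the drug stays prior.

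The grid shows that the result is certain within the pattern. It says nothing about how often the pattern occurs. A subject first dosed in January cannot show it, because the first-dose year then has no earlier month.

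**The case against.** The strongest reply is that this is a rare record with little consequence, and most of that stands. The pattern needs an unknown start month together with a known stop month, both in the first-dose year. In the example the true start is at most 78 days before dosing (1 January to 20 March). Protocol 9.4.6 asks for initiation and discontinuation dates, and Protocol 12.2 describes programmatic checks at data entry. The documents give no rate of partial dates, so any count would only be an assumed rate multiplied by 1000 subjects.

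Four stronger readings are tempting, and the documents do not support them.

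- *Any drug stopped in a month before dosing is re-dated.* Only the pattern above is.
- *The concomitant acne medication table is inflated.* That follows under the Protocol 11.7.2 definition. Under the literal SAP Section 8 wording the record drops out of both tables.
- *Subjects who washed out correctly are lost from the per-protocol population.* SAP 6.4 does not say that its list uses imputed dates, and a Clinical Representative reviews the list before unblinding. The effect is possible, not shown.
- *Month-end imputation of a stop in the first-dose month is the same error.* There the true stop may fall on either side of first dose, and month-end is an ordinary conservative convention.

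Conservatism does not defend the tie rule itself. A conservative imputation fills in what is unknown; this one replaces a known month. SAP 16.7, for adverse events, and 16.8.1 both let a complete stop prevail over an imputed start.

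**Conclusion.** The contradiction is real and the stated order settles it the wrong way. Within one narrow pattern every record is misdated: a year-only start in the first-dose year, with a stop that lacks only its day and falls in a month before the first-dose month. The drug loses its prior status and becomes concomitant or unclassified, depending on which document's definition is programmed.

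The reach is the prior and concomitant medication tables, including acne medications, and possibly the per-protocol review list. The number of records cannot be derived from the documents; that it is small is a judgement from how narrow the pattern is. The ITT co-primary analyses do not use these dates and are not affected. This is a minor point, worth correcting because it is cheap.

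**What to change.** In SAP 16.8, for records with both dates incomplete, either impute the stop date first or state that the 16.8.1 rule prevails, so that an imputed start later than the stop is set to the stop. In 16.8.2, limit the overwrite of the stop to records with a complete (nonimputed) start date.

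One mirror case should be covered in the same edit. If a start month is recorded after the last-dose month and the stop is known only to that same year, the amended rule would pull the start back to the last-dose date, outside its recorded month. Adding that neither rule may move a date outside its recorded month or year settles it. Such records should be uncommon, since routine collection ends with the final visit.

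The cost is two or three sentences and a small programming change before database lock, with no new data. Nothing conservative is lost in the affected pattern, because the recorded stop month is already before treatment. The SAP Section 8 gap for a start on the first-dose day is a separate wording matter that this change does not close.
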